Specify your research question(s), study aims or hypotheses (do not indicate "see protocol")

Surgical site infections are a subset of healthcare-associated infections (HAIs) that affect 3-5% of all patients undergoing surgery and are associated with a 2-fold increase in patient morbidity and mortality, a 2-fold increase in hospital duration, and a 66% increase in the risk of intensive care unit (ICU) admission (1-4). The Centers for Disease Control (CDC) and the World Health Organization (WHO) consider HAIs as a devastating issue tied to antibiotic resistance and have highlighted three major goals for HAI prevention including the following: 1) Prevention of infections in patients undergoing surgery, 2) Prevention of patient-to-patient bacterial transmission, and 3) improvement in antibiotic stewardship (5-7). These recommendations apply to the perioperative arena where the contribution of intraoperative bacterial reservoirs to bacterial transmission events and postoperative infection development has been confirmed (8-10). Indeed, a multicenter study recently demonstrated that stopcock contamination occurred in 23% of surgical cases, was associated with increased mortality, and was linked by molecular typing to postoperative infection (9). Intraoperative bacterial reservoir isolates have also been directly linked to the causative organism of infection for 30% of 30-day postoperative HAIs. Finally, transmission of S. aureus has been confirmed in up to 39% of surgical cases and has been directly linked to postoperative infection development(11). As such, attenuation of perioperative S. aureus transmission is an important target for HAI reduction. Therefore, our primary objective is to reduce perioperative S. aureus transmission. Our

secondary objective is to examine the impact of reduced *S. aureus* transmission on the incidence of superficial and deep surgical site infections (SSIs).

I.6 ***Background and significance and/or Preliminary studies related to this project. (do not indicate "see protocol")***

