Reducing Perioperative S. aureus Transmission via use of an Evidence-Based, Multimodal Program Driven by an Innovative Software Platform (OR PathTrac)

9/20/2018

Statistical Analysis

Multiple statistical methods were used. For simplification, we list the statistical methods in the precise sequence they are reported in the results.

The Fisher exact test was used to compare patient and procedural demographic information for treatment vs control groups and for cases involving *S* aureus transmission. Similarly, the distribution of patients by ASA scores greater than 2 and by sex for enrolled vs eligible patients were compared by surgeon using the Mantel-Haenszel test.

The Fisher exact test was also used to examine the potential association of each of the covariates mentioned earlier with *S aureus* transmission. None were associated.

A 2-sided Wilcoxon-Mann-Whitney test was used to examine the association of treatment assignment with the number of transmitted *S aureus* isolates. Poisson regression was used to estimate the incidence risk ratio (IRR) of *S aureus* transmission for the independent variable of treatment. Poisson regression was used to estimate the IRR because the incidence of transmission was so large (ie, much greater than 10%) that the odds ratio estimated using logistic regression would be a biased estimator of the relative risk.²⁴ We repeated the analysis using multilevel Poisson regression clustering by surgeon or specialty.

The Fisher exact test was used to compare the proportion of patients in the treatment group with transmission events before vs after surveillance feedback and the proportion of patients with SSI with and without documented *S aureus* transmission. Poisson regression was used to compare the proportion of patients with SSI with and without documented *S aureus* transmission, clustered by surgeon.

The proportion of patients with SSIs was compared with the Fisher exact test. Time to infection was evaluated by Cox proportional hazard modeling. We repeated the analysis using multilevel Poisson regression clustering by surgeon and specialty.

There were no missing data for the primary and secondary outcomes. Calculations were performed using Stata version 16.1 (StataCorp). All P values were 2-sided, and P < .05 was taken to indicate statistical significance.

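### The SAP applies two-sided P < .05 to four separate questions without a testing rule that follows the protocol's primary and secondary ranking

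*SAP*

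**What the plan says.** Protocol I.4 names transmission events as the primary outcome. I.5 gives reduced transmission as the primary objective and the effect of reduced transmission on superficial and deep SSI as the secondary one. XI.2 describes one unadjusted primary intention-to-treat comparison of transmission by arm, and its power figures concern transmission only.

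The SAP (Statistical Analysis) mentions primary and secondary outcomes but does not list them or give an order of testing. Apart from the demographic and covariate tests, it covers four questions:

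1. Transmission by arm: "A 2-sided Wilcoxon-Mann-Whitney test was used to examine the association of treatment assignment with the number of transmitted" isolates, followed by Poisson and multilevel Poisson models.
2. SSI: "The proportion of patients with SSIs was compared with the Fisher exact test. Time to infection was evaluated by Cox proportional hazard modeling", with a multilevel Poisson repeat. The groups are not named; by arm is the natural reading, but it is an inference.
3. SSI by transmission status: "the proportion of patients with SSI with and without documented" transmission, by Fisher and by clustered Poisson.
4. Feedback: "the proportion of patients in the treatment group with transmission events before vs after surveillance feedback", by Fisher.

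One sentence governs them all: "All P values were 2-sided, and P < .05 was taken to indicate statistical significance". Neither document gives a gate, an alpha split or an exploratory label.

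**The concern.** Ranking outcomes does not by itself control error. Under the SAP's sentence, an SSI result at P = .04 is statistically significant whether or not transmission differs between arms, and so is a before-after feedback result. The secondary objective in I.5 also does not say which contrast answers it, so either the randomised SSI-by-arm comparison or the observational SSI-by-transmission comparison could be cited. SSI is the outcome most likely to influence practice, so readers need to know which infection result, if any, is confirmatory and on what condition.

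**Working it through.** **The plan's own figure.** No family-wise error rate is stated. The nearest figure is the 98% power in XI.2 (40% v 28%, 500 per arm, no variation between service lines). XI.2 gives no alpha, so the SAP's two-sided 0.05 is used:

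power = Φ[(|p1 − p2| − 1.96√(2p̄q̄/n)) / √((p1q1 + p2q2)/n)], with p̄ = 0.34 and q̄ = 0.66.

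= Φ[(0.12 − 1.96 × 0.02996) / 0.02972] = Φ(2.06) = 0.980.

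The 98% is reproduced for one transmission contrast at 0.05.

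**Independent tests, all nulls true.** P(at least one) = 1 − 0.95^k.

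- Primary only: 5%.
- Primary plus SSI by arm: 1 − 0.95² = 9.75%.
- The three non-primary questions: 1 − 0.95³ = 14.3%.
- All four: 1 − 0.95⁴ = 18.5%. The Bonferroni upper bound is 4 × 0.05 = 20%.
- A non-primary result significant while the primary is not: 0.95 × 0.1426 = 13.5%.

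**Correlation.** For four equally correlated normal statistics, the 18.5% becomes 18.4% at correlation 0.1, 17.4% at 0.3 and 15.5% at 0.5.

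**Simulation of the four comparisons on shared data.** Inputs: 500 first patients per arm (XI.2); transmission 10.58% or 40% (both from XI.2); SSI 3% or 5% (ends of the range in I.5). Assumptions: feedback begins at the midpoint of the treatment arm, patients are independent, all nulls are true. There were 4,000 trials per scenario, so the Monte Carlo standard error is about √(0.18 × 0.82/4000) = 0.6 points.

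| Transmission, SSI | Any of four, all chi-squared | Any of four, all Fisher |
|---|---|---|
| 10.58%, 5% | 18.3% | 14.3% |
| 40%, 5% | 18.2% | 14.6% |
| 40%, 3% | 18.6% | 14.4% |

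The Fisher column is lower because that test is conservative at these rates. The SAP does not use Fisher for transmission by arm, so this column is a low end. A second simulation closer to the SAP's mix counted every test listed within a question, except that unclustered Poisson tests stood in for the clustered and multilevel models and a log-rank test for Cox. With transmission 11% or 40%, it gave 16.7-17.6%. Together these give about 14-19%.

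**Primary plus SSI by arm.** With chi-squared for transmission (XI.2) and Fisher for SSI (SAP), the simulated single-test sizes combine as follows:

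- 1 − (1 − 0.04925)(1 − 0.0370) = 8.4%
- 1 − (1 − 0.0495)(1 − 0.03225) = 8.0%
- 1 − (1 − 0.0505)(1 − 0.0330) = 8.2%

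With the 9.75% above, the range is about 8-10%.

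**SSI by arm alone.** Fisher rejected in 3.3-3.6% of null trials in the second simulation. At least one of its three SSI-by-arm tests rejected in 4.7-5.4%. Repeating SSI by arm in three models adds little; the inflation comes from having separate questions.

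**The case against.** The best defence is that the trial has a designated primary comparison, that neither document promises 5% across a family, and that the other results would be read as supporting. SSI by transmission is an observational association. The feedback comparison is a within-arm process check that suits the plan-do-study-act design (VII.E.6, XI.1). The secondary objective is worded as an examination, and only transmission was powered. Much of this stands, and it rules out several stronger readings that a reader might infer:

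- **That there is no hierarchy.** The outcomes are ranked. What is missing is a testing rule tied to the ranking.
- **That the trial's error rate is some 17% where 5% was claimed.** No 5% family-wise claim exists. A rate of that size needs all four nulls to be true and all four results to be read as confirmatory. I.5 and I.6 already regard transmission as linked to infection, so the third null is one the protocol does not believe. Without it, three independent tests give 14.3%; without the feedback check as well, 9.75%.
- **That SSI is left without error control.** The SSI-by-arm comparison alone stays near 5%. An association between SSI and transmission would not in itself be a claim that the bundle prevents infection.

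The calculations also treat patients as independent although service lines are randomised (VI.13), so they isolate multiplicity and are not this trial's actual error rate.

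The defence does not supply the missing label. Nothing in the SAP marks the last three questions as supporting or exploratory, and its significance sentence treats them exactly like the primary.

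**Conclusion.** The point holds in limited form. The SAP lets any of four questions be called significant at two-sided 0.05, with no order, gate or exploratory label. Read as four confirmatory claims, with all nulls true and patients independent, that means about 14-19% of trials with at least one false positive, and about 8-10% for the primary and SSI by arm. The primary contrast keeps its nominal 5%, apart from clustering and the choice among its tests, which are separate matters. The point bears on what may be claimed from the non-primary results and does not undermine the primary comparison. It should be corrected, but it is not a fatal flaw.

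A reader might also infer that adding a testing sequence now would give prespecified control. The SAP is in the past tense and already reports findings: no covariate was associated with transmission, and no primary or secondary outcome data were missing. If the data had been seen, the rule can discipline the claims but cannot count as planned in advance.

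**What to change.** Replace the general significance sentence in the SAP with the following:

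- Test one primary transmission contrast by arm at two-sided 0.05, naming the test. XI.2 has a chi-squared test and the SAP opens with Wilcoxon, so one must be chosen.
- Only if that is significant, test SSI by arm at two-sided 0.05 with one named test, stating that the groups are the randomised arms.
- Label the other SSI-by-arm models as sensitivity analyses.
- Label SSI by transmission status and before-versus-after feedback as exploratory, reported as estimates with 95% confidence intervals and no significance claim.

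If both nulls are true, a false claim requires the primary test to reject, so the rate is 5%. If only the SSI null is true, it is at most 5%. Both statements assume that each test is valid. The primary gives up no alpha.

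The cost is wording; no patients, data or further analyses are needed. The downside is that SSI cannot be claimed as confirmed if transmission is not significant, and two comparisons lose their significance claim. The SAP should state when the rule was adopted. If that was after the data had been seen, it should describe the rule as governing the claims made, not as prespecified error control.
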